2.6 Study Endpoints

2.6.1 Primary Endpoint

- Mean change from baseline in haemolysis markers as measured by reduction of indirect bilirubin after 8 weeks of treatment.

2.6.2 Secondary Endpoint(s)

- Mean change from baseline in haemolysis markers as measured by direct and total bilirubin, LDH, potassium, Hb and free haptoglobin after 8 weeks of treatment.
- Frequency and severity of reported or observed adverse events (AEs) by system organ class (SOC) and preferred terms (PTs) using Medical Dictionary for Regulatory Activities (MedDRA) coded terms, indicating seriousness criteria and relatedness over 8 weeks of treatment.

2.6.3 Exploratory Endpoint(s)

- Changes in haemolysis markers as measured by indirect, direct, and total bilirubin, LDH, potassium, Hb, and free haptoglobin, from baseline after 2, 4, and 6 weeks of treatment and 4 weeks after end of treatment (EoT).
- Frequency and severity of reported or observed AEs by SOC and PTs using MedDRA coded terms, indicating seriousness criteria and relatedness up to 4 weeks after EoT.
- Changes in clinical laboratory safety tests (serum biochemistry, safety haematology, and urinalysis) from baseline, 12-lead ECG, physical examination findings, vital signs (blood pressure, pulse rate), and haematological changes due to iron-restricted erythropoiesis after 2, 4, 6, and 8 weeks of treatment and 4 weeks after EoT.
- Changes in haematological indices, including Hb concentration, RBC count, Hct, MCV, MCH, MCHC, CHCM, RBC distribution width, WBC analyses including differential WBC counts, platelet and reticulocyte counts, percentage reticulocytes, percentage hypochromic microcytic RBCs (RBC volume versus Hb scatterplot analysis), from baseline after 2, 4, 6, and 8 weeks of treatment and 4 weeks after EoT.
- Changes in blood inflammatory markers as measured by high sensitivity C-reactive protein, interleukin 1 and interleukin 6, tumour necrosis factor alpha, soluble vascular cell adhesion molecule 1, endothelin-1, soluble platelet-selectin, and xanthine oxidase, from baseline after 2, 4, 6, and 8 weeks of treatment and 4 weeks after EoT.
- Assessment of iron-related parameters and markers of erythropoiesis: total serum iron, serum ferritin, serum transferrin, calculated TSAT, hepcidin, and erythropoietin, from baseline after 2, 4, 6, and 8 weeks of treatment and 4 weeks after EoT.
- VIT-2763 PK parameters (maximum concentration (C_{max}), clearance, distribution volume, area under the curve (AUC)). Sparse sampling for determination of VIT 2763 plasma concentration following multiple dosing will be obtained from pre-dose trough to 2 hours, 4 hours and 6 hours post-morning dose at study Visit V4. A population PK approach will be applied to estimate PK parameters.

- Change in patient reported outcomes using ASCQ-Me from baseline after 2, 4, 6 and 8 weeks of treatment.
- Changes in abnormal RBCs (sickling) assessed by peripheral blood smear from baseline after 2, 4, 6 and 8 weeks of treatment and 4 weeks after EoT.
- Number of VOC episodes and visceral infarctions over 8 weeks of treatment and 4 weeks after EoT.

3 HYPOTHESES AND DECISION RULES

3.1 Statistical Hypotheses

Due to the exploratory nature of this trial, no formal power calculations will be performed and therefore no statistical hypothesis testing has been defined.

3.2 Statistical Decision Rules

There is no formal statistical decision rule for this study, and all analyses are considered descriptive.

4 ANALYSIS SETS

In accordance with ICH E3 [1] and E9 [2] guidelines, the analysis sets are defined as follows:

4.1 Safety Set

The safety set consists of all randomised subjects under protocol version 3.0 or higher who have taken at least one dose of IMP. The subjects in the safety set will be analysed based on the treatment they received, regardless of randomisation.

The actual treatment is determined as the highest dose dispensed during the study for subjects who have taken at least one dose of IMP. More precisely:

- If the highest VIT-2763 kit dosage dispensed during the study is 30 mg, then the actual treatment will be “Cohort 1: VIT-2763 60 mg BID”.
- If at least one VIT-2763 kit of 60 mg dosage is dispensed during the study AND the maximum number of VIT-2763 kits dispensed during a visit is ≤ 3 , then the actual treatment will be “Cohort 2: VIT-2763 120 mg BID”.
- If at least one VIT-2763 kit of 60 mg dosage is dispensed during the study AND the maximum number of VIT-2763 kits dispensed during a visit is 4, then the actual treatment will be “Cohort 3: VIT-2763 120 mg TID”.
- If only placebo kits are dispensed during the study, then the actual treatment will be “Cohort 4: Placebo”.

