8.9 Allowed Adaptations in Case of Extraordinary Events, e.g., COVID-19

Extraordinary events may call for specific measures to maintain subject safety and guarantee conduct of clinical investigations according to established general and specific guidelines and regulations to meet agreed regulatory, quality, and scientific expectations.

For this, the following adaptations are considered for specific situations:

- Site visits are not possible within the defined time window, possibly leading to delayed:
 - Physical examination: consultation by local physician, follow-up assessment and guidance on drug adaptations via phone, remote visits at subject's home (e.g., home nursing)
 - Laboratory assessments: consultation by local physician, visit at local laboratory for blood analysis, or via home nursing
 - Adaptation of IMP: dispense sufficient amount of IMP at previous visit, delivery to subject's home by qualified designee as assigned by the Principal Investigator, or consider handover of IMP to relatives if allowed and in compliance with the applicable International Council for Harmonisation (ICH) Good Clinical Practice and other applicable laws and regulations, phone call by treating physician to guide dose adaptation of drugs
 - On-site monitoring: accept delayed on-site monitoring, conduct remote monitoring
 - On-site auditing: accept delayed on-site auditing, conduct remote auditing
 - AE/SAE/special situation reporting: frequent phone call visits
- Site visits are not possible within the defined time window, possibly leading to no:
 - Physical examination: consultation by local physician, follow-up clinical assessment via phone remote visits at subject's home (e.g., home nursing)
 - Laboratory assessments: consultation by local physician, local laboratory for blood analysis, or via home nursing
 - Adaptation of IMP: dispense sufficient amount of IMP at previous visit, delivery to subject's home by qualified designee as assigned by the Principal Investigator, or consider handover of IMP to relatives if allowed and in compliance with the applicable ICH Good Clinical Practice and other applicable laws and regulations, phone call by treating physician to guide dose adaptation of drugs

- On-site monitoring: accept delayed on-site monitoring, conduct remote monitoring
- On-site auditing: accept delayed on-site auditing, conduct remote auditing
- AE/SAE/special situation reporting: frequent phone call visits

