4.3 Per-Protocol Set

The per-protocol set (PPS) consists of all subjects who, in addition to the ITT criteria, completed the study and had no major protocol deviations impacting the primary objective of the trial (as defined in the protocol deviation plan and finalised during the blind data review meeting). Subjects with a study drug compliance (see Section 5.6) lower than 80% of prescribed doses or upper than 110% of prescribed doses will be considered as major deviations.

Subjects who did not complete the study as per protocol as indicated in study termination CRF form or who discontinued the treatment prematurely as recorded in treatment termination form will be considered as not having completed the study and will then be excluded from PPS in addition to subjects with major protocol deviations. The subjects will be analysed based on the treatment they were randomised to.

4.3.1 *Protocol deviations*

All subjects with major protocol deviations impacting the primary objective as defined in the latest protocol deviations plan will be excluded from PPS. They will be reviewed during the blind data review meeting.

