5.6 Study Drug Exposure and Compliance

The following durations of study drugs (including VIT-2763 and Placebo) will be computed in days:

Duration of study drug (in days) = Treatment stop date – Treatment start date + 1

Treatment start and stop dates will be derived as defined in Section 5.1.4.

The total amount of VIT-2763 taken in mg will be calculated for each subject from the difference between the amount of VIT-2763 dispensed in mg and the amount of VIT-2763 returned in mg. It will be compared to the amount expected to be taken for subjects randomised in a VIT-2763 cohort to calculate the percentage compliance to VIT-2763. Derivation details are provided below.

Total amount of VIT-2763 (mg) = $30 * (\text{Number of VIT-2763 30 mg capsules dispensed} - \text{Number of VIT-2763 30 mg capsules returned}) + 60 * (\text{Number of VIT-2763 60 mg capsules dispensed} - \text{Number of VIT-2763 60 mg capsules returned})$.

The total amount of VIT-2763 taken will be computed for all randomised subjects and will be equal to 0 if no dispensation error occurred in Placebo cohort. In case of miss allocation for a patient receiving VIT-2763 instead of Placebo, the amount will be counted for VIT-2763.

Expected amount of VIT-2763 (mg) for cohort 1 = $120 * (\text{Duration of study drug in days} - 1) + 60$.

Expected amount of VIT-2763 (mg) for cohort 2 = $240 * (\text{Duration of study drug in days} - 1) + 120$.

Expected amount of VIT-2763 (mg) for cohort 3 = $360 * (\text{Duration of study drug in days} - 1) + 120$.

VIT-2763 compliance (%) = $(\text{Total amount of VIT-2763 (mg)} / \text{Expected amount of VIT-2763 (mg)}) \text{ for cohort 1-2-3} * 100$.

The total number of capsules of study drug (VIT-2763 or Placebo) taken will be calculated for each subject from the difference between the total number of capsules dispensed and the total number of capsules returned. It will be compared to the expected number of capsules to be taken by subject to calculate the percentage compliance to study drug.

Total amount of study drug (number of capsules) = Number of capsules dispensed - Number of capsules returned

Expected amount of study drug (number of capsules) for cohorts 1, 2, 4a = $4 * (\text{Duration of study drug in days} - 1) + 2$

Expected amount of study drug (number of capsules) for cohort 3, 4b = $6 * (\text{Duration of study drug in days} - 1) + 2$

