5.7 Efficacy Analyses

5.7.1 Primary Efficacy Analysis

The changes in indirect bilirubin from baseline to Visit 6 (after 8 weeks of treatment) will be summarised using standard descriptive statistics for continuous variables with 95% confidence interval (CI) of the mean on the ITT population by randomised treatment groups as described in Table 5.

Analysis visit windows will be considered for the primary efficacy analysis (see Section 5.1.2). The analysis will be repeated on the PPS by actual treatment group and on mITT if applicable.

Three sensitivity analyses will be run on the ITT population as the primary analysis, with the imputation of the missing data due to haemolised samples at baseline or Visit 6 (see section 5.1.9). Analyses will be:

- Imputation of missing baseline with the median of the non-missing baseline of the pooled subjects. Imputation of Visit 6 missing data using the minimal value within the same cohort.
- Imputation of missing baseline with the median of the non-missing baseline of the pooled subjects. Imputation of Visit 6 missing data using mean value within the same cohort.
- Imputation of missing baseline with the median of the non-missing baseline of the pooled subjects. Imputation of Visit 6 missing data using maximum value within the same cohort.

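### SAP 4.1 tells 120 mg BID from 120 mg TID by the largest kit count at one visit, so extra or extended supply can give a correctly treated subject the wrong actual-treatment label, or none

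*SAP*

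**What the plan says.** SAP 4.1 bases the as-treated label on supply: "The actual treatment is determined as the highest dose dispensed during the study". A subject whose strongest active kit is 30 mg is Cohort 1, and one given only placebo kits is placebo. Once any 60 mg kit has been dispensed, the kit count alone decides. The subject is Cohort 2 (120 mg BID) if "the maximum number of VIT-2763 kits dispensed during a visit is ≤ 3" and Cohort 3 (120 mg TID) if "the maximum number of VIT-2763 kits dispensed during a visit is 4". No other count is covered.

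Protocol 8.9 lists measures for extraordinary events that prevent a site visit within its window. One is to "dispense sufficient amount of IMP at previous visit".

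The label is used for the safety-set tables (SAP 5.8). For the per-protocol set (PPS), the SAP gives two answers. Section 4.3 says: "The subjects will be analysed based on the treatment they were randomised to". Section 5.7.1 says: "The analysis will be repeated on the PPS by actual treatment group and on mITT if applicable". SAP 5.1.1 bases PPS percentages on actual treatment groups, SAP 5.7.2, 5.7.3, 5.9.1 and 5.9.2 repeat the PPS analyses by actual treatment, and protocol 12.4.2 groups the PPS by treatment received.

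**The concern.** Cohorts 2 and 3 use the same 60 mg capsule (protocol Table 3), so the count at one visit is all that separates the two regimens under this rule. A kit count measures quantity, and quantity depends on days covered as well as capsules per day. A BID subject supplied for a longer gap can therefore look like a TID subject supplied for a normal one.

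At stake is the content of the 120 mg TID column. The completed studies described in protocol 1.4 and 2.3.1 used once-daily or twice-daily dosing, so this trial supplies the TID safety data. With six subjects planned per active arm, one wrongly placed subject is visible in every by-dose adverse event, laboratory, ECG and vital-sign table.

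**Working it through.** **Inputs**
- Capsules per day, from SAP 5.6: "Expected amount of study drug (number of capsules) for cohorts 1, 2, 4a" is 4 × (days − 1) + 2, so 4 per day for BID. "Expected amount of study drug (number of capsules) for cohort 3, 4b" is 6 × (days − 1) + 2, so 6 per day for TID.
- Dispensing interval D: nominally 14 days (protocol synopsis, visits V3 to V6). Values from 13 to 22 days were also tried, to allow for visit windows.
- Capsules per kit c: not stated. Protocol 6.2.1 gives only the bottle volume. Sizes from 10 to 120 were tried.
- Planned arm size: 6 per active cohort.

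**What the cut-off implies.** Kits per visit = capsules needed ÷ c, rounded up. If a correctly supplied TID subject gets exactly 4 kits, then 3 < 6D/c ≤ 4. Multiplying by 4/6 gives 2 < 4D/c ≤ 2.67, so the BID subject gets 3. The SAP's cut-off is consistent with this. It cannot be reproduced outright because c is unknown, but it is attainable, for example with 21 to 27 capsules per kit at D = 14, or 27 to 35 at D = 18. The result of 3 held for every interval tried, and also when one overage kit per visit was added.

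**Applying the rule from 3 (BID) and 4 (TID) kits**

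| Correctly treated subject | Kits at that visit | SAP 4.1 label |
|---|---|---|
| BID, routine supply | 3 | BID |
| BID, one extra kit | 3 + 1 = 4 | TID |
| BID, 1.5 times the interval | 4 × 1.5D/c = 6D/c, so 4 | TID |
| BID, double supply | 8D/c lies in (4, 5.33], so 5 or 6 | none |
| TID, one extra kit | 4 + 1 = 5 | none |
| TID, double supply | 12D/c lies in (6, 8], so 7 or 8 | none |

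The third row is the clearest case. At D = 14, BID for 21 days needs 4 × 21 = 84 capsules, and TID for 14 days needs 6 × 14 = 84. The rule cannot tell them apart. If routine supply covers a longer D, the trigger moves to 1.5D days.

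**If BID supply is not 3 kits.** At 2 kits, one extra gives 3 (still BID) and a double supply gives 4 (TID). At 1 kit, neither changes the label.

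**Would the subject stay in the PPS?** Expected BID capsules over 56 days are 4 × 55 + 2 = 222. An extra kit returned unopened leaves compliance unchanged, so the subject stays in. An unreturned kit of 21 capsules gives (222 + 21)/222 = 109.5%, inside the 110% limit. One of 24 gives (222 + 24)/222 = 110.8%, which excludes the subject.

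**Effect of one relabel.** BID and TID go from 6 and 6 to 5 and 7. If the moved subject has the only event, 1/6 (16.7%) under BID becomes 0/5 under BID and 1/7 (14.3%) under TID. If the only event is in a remaining BID subject, 1/6 becomes 1/5 (20.0%). The TID mean moves by one seventh of the difference between that subject and the mean of the six TID subjects.

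**The case against.** Five points can be made in the rule's defence.

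1. *Kits per visit are unknown.* The cut-offs presumably come from supply specifications not shown here. This stands. A reader might infer that mislabelling follows whatever the kit size, but it does not: at one BID kit per visit neither an extra kit nor a double supply relabels anyone. What needs no assumption is that five or more kits has no label.
2. *A full double supply leaves a blank, not TID.* This also stands. From 3 kits, doubling gives 5 or 6, and a programmer would notice the missing value. It does not cover a partial extension: 1.5 times the usual interval gives exactly 4 kits and a silent TID label.
3. *The trigger may be rare.* Neither document describes routine spare kits, protocol 8.9 is limited to extraordinary events, and home shipment under protocol 6.6.1 may not count as dispensing at a visit. Frequency is unknown.
4. *The reach is limited.* A reader might infer that the primary result is exposed. It is not: SAP 5.7.1 analyses the ITT population by randomised group, and the PPS is a repeat that is unaffected if SAP 4.3 governs. The pooled All VIT-2763 column does not change, ECG plots are by randomised cohort, and the SAP 5.2 count of subjects treated differently from their randomisation might expose a false relabel. If that count uses the 4.1 label, though, it would report a misallocation that never happened.
5. *Kit strength cannot replace the count*, because both 120 mg regimens use 60 mg kits. This is right, and the fix must allow for it.

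**Conclusion.** The weakness is real, and the SAP should be changed. The rule has no label for five or more kits, whatever the kit size. If routine supply is 4 kits for TID and 3 for BID, which the cut-off implies but neither document states, it also labels a correctly treated BID subject as TID after one extra kit or about 21 days' supply. The by-dose safety tables are exposed. The PPS repeats are exposed only where SAP 5.1.1, 5.7 and 5.9 are followed over SAP 4.3.

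The expected effect is small: one relabel gives arms of 5 and 7 in a descriptive study with no tests or decision rules, and how often it would happen cannot be judged from the documents. They do not support saying that it has happened or that the ITT primary analysis is at risk.

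The conflict over PPS grouping stands by itself. The SAP's precedence over the protocol (SAP 1) does not settle it, because the SAP disagrees with itself. It matters only when actual and randomised treatment differ, which a false kit-count label would bring about.

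**What to change.** In SAP 4.1, set actual treatment to the IWRS-assigned regimen by default. Reclassify only for a documented dispensing error, meaning a wrong kit type or strength, or capsules per day supplied over the days covered that do not match the assigned regimen. The capsules-per-day check is needed because strength alone cannot separate the two 120 mg regimens. State that advance or extra supply does not change the regimen, so that every kit count leads to a label.

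Separately, choose one grouping rule for the PPS and use it in SAP 4.3, 5.1.1, 5.7 and 5.9, reconciled with protocol 12.4.2. As randomised or as received can each be defended. If the choice differs from the protocol, record it under SAP 1.2, which at present mentions only additional analysis sets.

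The cost is SAP wording and a short change to one derived variable. Assignment is held in the IWRS, and capsules dispensed and returned are already used for compliance in SAP 5.6, so no new data collection should be needed.

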4.2 Intent-To-Treat Population

The Intent-To-Treat (ITT) population consists of all subjects who are randomly assigned to a treatment group under protocol version 3.0 or higher. The subjects will be analysed based on the treatment they were randomised to.

4.3 Per-Protocol Set

The per-protocol set (PPS) consists of all subjects who, in addition to the ITT criteria, completed the study and had no major protocol deviations impacting the primary objective of the trial (as defined in the protocol deviation plan and finalised during the blind data review meeting). Subjects with a study drug compliance (see Section 5.6) lower than 80% of prescribed doses or upper than 110% of prescribed doses will be considered as major deviations.

Subjects who did not complete the study as per protocol as indicated in study termination CRF form or who discontinued the treatment prematurely as recorded in treatment termination form will be considered as not having completed the study and will then be excluded from PPS in addition to subjects with major protocol deviations. The subjects will be analysed based on the treatment they were randomised to.

4.3.1 *Protocol deviations*

All subjects with major protocol deviations impacting the primary objective as defined in the latest protocol deviations plan will be excluded from PPS. They will be reviewed during the blind data review meeting.

4.4 Other Analysis Sets

For the purposes of subjects' disposition tables and listings an additional analysis population is defined:

- **Randomized population:** all subjects who are randomly assigned to any treatment group under protocol version 3.0 or higher.
- **Enrolled population:** all subjects who have signed informed consent on any protocol version.
- **Advanced Intent-To-Treat Set:** The advanced ITT (aITT) population consists of all subjects who are randomly assigned to any treatment group under any protocol version. The subjects will be presented based on the treatment they were randomised to.

The following analysis set may also be defined:

- **Modified Intent-To-Treat Set (optional):** The modified ITT (mITT) will consist of all subjects of ITT with no major Coronavirus Disease of 2019 (COVID-19) related protocol deviation (as defined in the protocol deviation plan and finalised during the blind data review meeting). This population may be used depending of the number of subjects with major COVID-19 related-protocol deviations and the potential impact on the analyses. Decision to use or not this analysis set for sensitivity analyses will be taken during the blind data review meeting and it will be documented in the blind data review minutes before unblinding.

The **analysis population for PK** will be described in a separate document.

5 DESCRIPTION OF THE STATISTICAL ANALYSIS

This section describes the statistical analyses, presentation of the results, and the study endpoints/measures that will be collected and/or derived during the study at the time points specified in the Schedule of Events (see Section 2.3).

5.1 General Considerations

The software used for all summary statistics and statistical analyses will be SAS® Version 9.4 or later (SAS Institute, Inc.).

MedDRA [Version 24.0] and the current version of the World Health Organization Drug (WHO Drug) dictionary [Mar2021 B3] will be used for coding.

Derived datasets will be generated by the Labcorp/Covance Biostatistics and Programming Department from the Clinical Interchange Standard Consortium (CDISC) Study Data Tabulation Model (SDTM [version 3.3]) datasets in accordance with CDISC ADaM version 2.1 and the ADaM Implementation Guide v1.1.

All blinded study team members will remain blinded to the randomisation arms until complete cleaning of the data and blind data review meeting. For the final analysis after final database lock the blinded statistical team will be unblinded according to the project specific unblinding plan and following sponsor approval. This does not concern the independent unblinded statistician responsible for the DSMB report preparation.

The final versions of the SAP (along with TFL shells documents) will be filed at trial completion in the electronic trial master file (eTMF) study documentation and eTMF plan will be followed for biostatistics documents filing.

The data collected for the one randomised subject under protocol version 2.0 will be listed only.

5.1.1 *Standard Descriptive Statistics*

Continuous Variables

Unless specified otherwise, the following standard descriptive statistics by treatment group will be obtained for continuous variables: number, mean, standard deviation, median, minimum and maximum. The minimum and maximum will be reported to the same number of decimal places as the raw data recorded in the database. Mean, median, and quartiles will be displayed to one more decimal place than collected value and standard deviation will be displayed to two more decimal place than the collected value.

Categorical Variables

Unless specified otherwise, the following standard descriptive statistics by treatment group will be presented for categorical values: total number of available values and missing values, number of values in each category and the corresponding percentage of the total number of values available will be calculated. The percentages will be displayed using one decimal.

Percentages will be calculated using the total subjects per randomised treatment group, except for outputs in the PPS and the safety set, where percentages are based on the total subjects per actual treatment group.

5.1.2 *Definition of Baseline*

The baseline value for a variable will be defined as the last available (non-missing) value before the first administration of study drug. Study day 1 is defined as the day of the first study drug administration. For analysis relative day, if considered date is before the first study drug administration date, then analysis relative day will be computed as date minus first study drug administration date, otherwise, it will be computed as date minus first study drug administration date + 1.

5.1.3 *Planned Assessment Windows*

Table 4 describes the analysis visit windows (i.e. the relative study day ranges) to be applied to the assessments or sample collections dates to determine the analysis visit.

Table 4 Planned and Analysis visits Windows

Analysis Visit Label	Target Day	Planned Visit Window (Protocol Specified)	Analysis Visit Window
Baseline	1	--	Before first IMP intake
Visit 3 (Day 14)	14	± 2 days	From Day 2 to Day 21
Visit 4 (Day 28)	28	± 4 days	From Day 22 to Day 35
Visit 5 (Day 42)	42	± 4 days	From Day 36 to Day 49
Visit 6 (Day 56)	56	± 4 days	From Day 50 to Day 70
Visit 7 (Day 84)	84	± 4 days	From Day 71 and higher

Assessments (planned and unscheduled) will be re-mapped into the analysis windows. For a parameter, the following rules will be applied:

- if several assessments fall into the same analysis window, the closest to the target day will be considered for the analysis.
- When there are 2 assessments closest to the target day, the latest one will be considered for the analysis.
- if several assessments are available at the selected day, the average of the values will be taken.

In all statistical tables by visit, the analysis visits will be considered. In listings presenting data by visit, both nominal and analysis visits will be provided.

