For treatment group dose intake day missing (or Unknown), the day will be imputed to the end day of the previous visit.

The original incomplete, missing or partial dates and corresponding imputed dates will be presented in the listings.

During the conduct of the study, a non-neglectable number of missing data for the primary endpoint (indirect bilirubin) have been observed at baseline and Visit 6. Sensitivity analyses will be performed for the primary endpoint with different imputations for the missing data. Only missing data due to haemolysed samples will be imputed as they can be considered as missing at random while missing data because of withdrawal of the study cannot. Imputations will be as following:

- Missing baseline data will be imputed with the median of the non-missing baseline indirect bilirubin of the pooled subjects of all cohorts.
- For missing data at visit 6, 3 types of imputation will be performed: the minimal value, the mean and the maximal value within the Cohort of the subject.

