5.7.3 Exploratory Efficacy Analysis

Summaries of values and changes from baseline for each haemolysis marker (indirect, direct and total bilirubin, LDH, potassium, Hb and free haptoglobin) will be reported for each visit using standard descriptive statistics for continuous variables on the ITT population by randomised treatment groups as described in Table 5. Analyses will be repeated on the PPS by actual treatment group and on mITT if applicable.

Summaries of absolute and percent changes from baseline for indirect bilirubin, CHCM and MCHC will also be reported for each visit using the same approach.

Number and percentage of subjects who had at least 20% reduction in Indirect Bilirubin from baseline will be summarized at each post-baseline visit.

Number and percentage of subjects who had at least 5% reduction in CHCM and MCHC from baseline will be summarized at each post-baseline visit.

Analyses will be repeated on the PPS by actual treatment group and on mITT if applicable.

For each haemolysis marker, 3 figures will be provided:

- Line plots by subject: individual marker values (y-axis) in function of target visit day (x-axis) joined by subject and plotted in separate windows for the randomised cohorts (1, 2, 3, 4).
- Line plots by subject in log scale: same plot as previous with individual marker values displayed in a \log_{10} scale (y-axis)
- Means with 95% CIs of changes from baseline marker values for the 4 randomised cohorts (y-axis) in function of target visit day (x-axis). Means will be joined by group.

All graphics will be done on the ITT.

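### Visit windows based on study day alone can place a follow-up sample taken 24–32 days off drug, unmarked, in the primary Week 8 table

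*SAP*

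**What the plan says.** The primary endpoint is the change in haemolysis markers "as measured by reduction of indirect bilirubin after 8 weeks of treatment" (SAP 2.6.1). SAP 2.6.3 makes the change in the same markers four weeks after end of treatment a separate, exploratory endpoint.

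SAP 5.1.3 assigns samples to visits by relative study day: "Assessments (planned and unscheduled) will be re-mapped into the analysis windows". In Table 4 the Visit 6 window is "From Day 50 to Day 70", with target Day 56. If several values fall in one window, the one closest to the target day is used. Neither rule looks at treatment status, last dose or nominal visit. SAP 5.1.3 adds: "In all statistical tables by visit, the analysis visits will be considered". SAP 5.7.1 confirms: "Analysis visit windows will be considered for the primary efficacy analysis" (its cross-reference is to 5.1.2, but the windows are in 5.1.3). The ITT population keeps every subject randomised under protocol version 3.0 or higher (SAP 4.2).

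Protocol 8.6 has the Visit 6/early-termination assessments done when a subject stops early. Protocol 8.7 follows everyone, including those who withdrew prematurely, for 28±4 days after end of treatment, and lists haemolysis markers among the Visit 7 activities.

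**The concern.** After a permanent stop before Day 50, a prompt early-termination sample is tabulated under an earlier visit. The Visit 7 sample can then be the only value in the Visit 6 window. The SAP defines that sample's timing as a different endpoint, yet the windows move it into the primary row. SAP 5.1.9 also declines to impute values missing because of withdrawal, since it does not regard them as missing at random. The window rule can fill that same gap with an off-drug value, without saying so.

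At stake is how the cohort summaries are read. The value also enters two other outputs:

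- the Visit 6 row of the table of subjects with "at least 20% reduction in Indirect Bilirubin from baseline will be summarized at each post-baseline visit" (SAP 5.7.3);
- the source for imputing haemolysed Visit 6 samples, which uses "the minimal value, the mean and the maximal value within the Cohort of the subject" (SAP 5.1.9).

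The study has no hypothesis test, so these descriptive cohort figures are its result.

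**Working it through.** **Inputs.** Target days 14, 28, 42, 56 and 84, and Visit 6 window Day 50–70 (SAP Table 4). Visit 7 at 28±4 days, that is 24 to 32 days, after end of treatment (Protocol 8.7). Six subjects per active cohort (SAP 2.2).

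**The plan's own figures.** The upper window limits are midpoints between targets: (14+28)/2 = 21, (28+42)/2 = 35, (42+56)/2 = 49, (56+84)/2 = 70. These match Table 4.

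**Which stops are affected.** Let s be the day of last dose, with a prompt early-termination visit and no other sample on Day 50–70. Visit 7 falls on Day s+24 to s+32.

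- At least one permitted day in the window: s+32 ≥ 50 and s+24 ≤ 70, so s = 18 to 46.
- All nine days in the window: s+24 ≥ 50 and s+32 ≤ 70, so s = 26 to 38.

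| Last dose (day) | Range of Visit 7 days | Permitted days tabulated as Visit 6 |
|---|---|---|
| 1–17 | 25–49 | 0 of 9 |
| 18–25 | 42–57 | 1 to 8 of 9 |
| 26–38 | 50–70 | 9 of 9 |
| 39–46 | 63–78 | 8 to 1 of 9 |
| 47–49 | 71–81 | 0 of 9 |

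For these stops the early-termination sample is tabulated as Visit 3 (stop on Day 18–21), Visit 4 (Day 22–35) or Visit 5 (Day 36–46). Example: after a stop on Day 28, Visit 7 falls on Day 52–60, exactly the planned days of an on-treatment Visit 6 (56±4). Subjects who complete on schedule (Day 52–60) have Visit 7 on Day 76–92 and are not affected.

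Counting day pairs for stops on Day 1–49: 13×9 + 2×(1+2+…+8) = 117 + 72 = 189, out of 49×9 = 441. This describes the calendar only. It is not the probability that an early stopper is affected.

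**Where stops could arise.** The stopping rules in Protocol 5.4.2 include haemoglobin, ferritin and ECG criteria, which are assessed at visits. The windows for Visit 4 (Day 24–32) and Visit 5 (Day 38–46) both lie inside Day 18–46.

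**Weight of one value.** 1/6 = 16.7% of a full cohort, 1/5 = 20% of a cohort with five usable values, 1/18 = 5.6% of the pooled active group. If a fraction f of the drug effect is lost by the time of sampling, the mean change in a cohort of six shrinks by f/6. The documents do not give f, so the range is 0 to 17%.

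**Imputation, as an illustration only.** Assume equal baselines, four on-drug changes of −1, one off-drug change of 0 (f = 1) and one haemolysed Visit 6 sample.

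- Minimum: (−4+0−1)/6 = −0.833, 17% short of −1.
- Mean: (−4+0−0.8)/6 = −0.800, 20% short.
- Maximum: (−4+0+0)/6 = −0.667, 33% short.

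With the off-drug value left out of the imputation source, all three give −0.833. The remaining 17% is the direct weight of that value in the table.

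**The case against.** Keeping a sample from around Day 56 whether or not drug was stopped is an ordinary ITT choice, and contiguous midpoint windows are conventional. Much can also be traced. By-visit listings show nominal and analysis visits (SAP 5.1.3), last-intake dates are listed and discontinuations tabulated (SAP 5.2), and the per-protocol repeat excludes early stoppers (SAP 4.3). With 24 subjects the affected values could be counted by hand. All of this stands, and it is why the ITT table should stay primary. It leaves a gap, however. No table counts these values. The per-protocol set also drops subjects with major deviations, including compliance outside 80–110%, so an ITT/per-protocol difference does not isolate the cause. Neither safeguard touches the imputation source.

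The trigger is narrow. After premature withdrawal, Protocol 8.7 sets adverse events and concomitant medications as the minimum, and Protocol 10.7.2 lets the final follow-up be a telephone call. The request for every effort in Protocol 5.4.1 concerns safety follow-up, in a paragraph about withdrawal for adverse events. A reader might infer that every early stopper must give a Visit 7 haemolysis sample; the documents do not say that.

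A reader might also infer that the drug effect is gone by then, because the half-life is 2–5 hours. That does not follow for a haemolysis marker. Protocol 2.2 treats serum iron as the acute effect and red-cell indices as the chronic one, and no washout time for bilirubin is given.

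**Conclusion.** The point holds as a gap in the windowing rule. For a permanent stop on about Day 18–46 (for every permitted Visit 7 day if the stop is on Day 26–38), a haemolysis value taken 24–32 days off drug can be tabulated as the primary Visit 6 value with no mark in the summary tables. This assumes a prompt early-termination visit, a usable Visit 7 sample and no other sample on Day 50–70.

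It is tempting to go further and say that the primary result is biased, or that 43% (189/441) of early stops are affected. The documents support neither. The number of such stops is not given and may be zero, the 189 of 441 weights all days equally, and the loss of effect off drug is unknown. What can be said is that one such value carries 1/6 of a full cohort's mean, or 17 percentage points in its responder row. A low-cost clarification before unblinding is worthwhile.

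**What to change.** Change the SAP only; the ITT table stays primary.

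1. **SAP 5.1.3.** Flag as off-treatment any nominal Visit 7 sample that maps to the Visit 6 window and comes from a subject who permanently discontinued study drug. Flag also any other value in that window taken more than a set interval after the treatment stop date. Use the recorded stop date only: where it is missing, SAP 5.1.4 substitutes the latest start date on the study treatment administration page, which can be too early and could flag genuine on-drug values. The sponsor should fix the interval before unblinding, on pharmacodynamic grounds and not from the drug's half-life.
2. **SAP 5.7.1 and 5.7.3.** Show the number of flagged values per cohort in the primary table and in the Visit 6 row of the indirect bilirubin responder table. Repeat the primary table without them. A count of zero would settle the matter.
3. **SAP 5.1.9.** Leave flagged values out of the cohort minimum, mean and maximum used to impute haemolysed Visit 6 samples.

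The cost is one derived flag, a count line and one repeated table with slightly fewer subjects (for example five instead of six in a cohort). The treatment stop date is already collected on the CRF. No protocol amendment or extra visit is needed.
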